Solius has created The Solius Photobiologic System (SPS), which is an experiential device that allows a user to receive a calibrated and calculated dose of vitamin D using wavelengths of UV light that facilitate the body's endogenous production of vitamin D and a variety of biologically controlled feedback mechanisms. The output of SPS is very similar to a NB-UVB device, but without the wavelengths that are less effective in endogenous vitamin D production. Exposure of individuals with varying skin types to these lights will enable us to observe the effect of artificial UVR exposure in creating vitamin D in individuals with varying shades of skin color. The benefit of this lamp will allow individuals who live in northern locations or individuals with malabsorption problems to create vitamin D.

Solius previously has completed two human clinical trials. The first study was a pilot feasibility study aimed to validate if the Solius Photobiological System efficiently stimulated the endogenous vitamin D process. The second study was a randomized non-inferiority study comparing the SOLIUS device to oral vitamin D supplements.

In a prospective cohort study (QR-TRP-002), six healthy adults with Fitzpatrick skin types I, II, and III were exposed to a 0.75 minimal erythema dose (MED) of UVB radiation to approximately 75% of their body surface area once per week for 4 weeks. The individual dose was determined with Fitzpatrick skin typing, followed by exposure of the underneath of one forearm to 10 successively increasing durations of exposure to UVB. The subjects had a significant increase in mean 25(OH)D from  $22.8 \pm 13.9$  ng/ml to  $27.2 \pm 12.0$  ng/ml ( $P<0.05$ ), representing a 19% increase over baseline after 4 weekly UVB exposures. No adverse events occurred.

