**Table 2. Outcomes measurement at each time point of the study for both study groups**

Activity	Baseline Wk 1	Titration					Intervention			
		Wk 2	Wk 3	Wk 4	Wk 5	Wk 6	Wk 7	Wk 8	Wk 9	Wk 10
Informed Consent	X									
Inclusion/Exclusion	X									
Medical History	X									
Demographics/ Skin typing	X									
UVB Exposure		X	X	X	X	X	X	X	X	X
25(OH)D	X	X					X			X
Sun exposure/ Vit. D food checklist	X	X								X
Concomitant Medications	X	X					X	X	X	X
Adverse Events		X					X	X	X	X

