## 6 Potential Risks and Benefits

### 6.1 Risks

The main acute adverse effects of narrowband UVB (NB-UVB) are erythema and induction of photosensitivity diseases, such as polymorphic light eruption (PLE). Although the risk of erythema episodes may be increased by concomitant phototoxic drugs, this can be minimized by undertaking a baseline minimal erythema dose (MED) and establishing treatment protocols based on an individual's MED. This also allows any unsuspected abnormal photosensitivity diseases to be detected, in particular solar urticaria or chronic actinic dermatitis (CAD). Induction of PLE may occur during a treatment course but generally can be accommodated via dose adjustments and judicious use of topical corticosteroid, without the need to stop NB-UVB. Other uncommon side-effects, such as psoriatic lesional blistering, occasionally occur but generally treatment is very well-tolerated.

Overexposure to our artificial UVB source may incur similar symptoms to a mild sunburn (slight reddish coloration to the skin). The Solius Photobiological System was designed to minimize total UVB exposure to minimize the potential for sunburn. To make sure subjects do not develop redness (erythema) or psoriatic lesional blistering, the exposure will set for the lamp to 60% or 0.60 of the minimal erythema dose (MED) for each individuals' skin type.

Over exposure to the UVB to the eyes may cause photokeratitis.

To prevent the overexposure, the subject's dosage will be determined during titration period. Eye protection will be provided to the subjects before each treatment. The device software will require subject confirmation that is in place before treatment can be delivered.

As the appropriate doses are individualized to the subject, to establish the correct dose, each subject will complete a titration period of up to 5 weeks. The titration period will start with an erythemally weighted dose of 10.53 mJ/cm^2 to 43.07 mJ/cm^2 (depending on skin type) and increase by 26 – 36%

each step until a maximum erythemally weighted dose of 34.88 mJ/cm^2 – 109.33 mJ/cm^2 (depending on skin type) or the subject shows a skin reaction. This dose will be the subject's dosage.

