### 7.2 Subject Exclusion Criteria

An individual who meets any of the following criteria will be excluded from participation in this study:

1. Ongoing treatment with supplemental or pharmacological doses of vitamin D, vitamin D metabolites or analogues
2. Pregnant
3. History of underlying photosensitivity
4. Use of medications that cause a photosensitivity reaction (including but not limited to): tetracycline, tretinoin, amiodarone, doxycycline, naproxen, diphenhydramine, methotrexate, and hydrochlorothiazide
5. History of skin cancer
6. Plan to received significant sun exposure below the 33rd parallel during study
7. Used tanning or phototherapy devices within the last 30 days
8. Vitamin D supplement use of more than 600 IU daily.

9. Systemic steroids use
10. H1 antihistamine use in the last 7 days
11. Diagnosed with light allergies (including but not limited to): actinic prurigo, polymorphous light eruption, or solar urticaria
12. Diagnosed with light sensitivities (including but not limited to): protoporphyria, photodermatitis, xeroderma pigmentosum, lupus erythematosus, chronic actinic dermatitis, or UV-sensitive syndrome

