Approximately 14 adult subjects with 5 skin types groups (I, II, III, IV and V/ VI) will be enrolled for vitamin D deficiency/ insufficiency screening. We expect at least 80% of the population in the Boston area has a level of 25(OH)D below 30 ng/ml. Thus, we will enroll approximately 14 subjects with different group skin types to enroll 10 vitamin D deficient or insufficient subjects in this study. All of the subjects will receive the UVB intervention. The device will have a strip of colored LED installed inside the light towers. Both UV lamps and colored LED will turn on during the treatment. To elaborate further, all subjects will use the same device with the exact same workflow on the touchscreen user interface. The experience in starting a SOLIUS session, answering the safety questions, automatic dispensing of eyewear, etc. will be the same for all subjects. This is achieved by adding an independent software branch to the existing system that replicates the user workflow code but only turn on the LED drivers. LED strips are added to the existing light tower, and the lights will project through the same light path as the UV lamps. As a result, visible purple light will be emitted from the same emitting window as the UV lamps.

Blood samples will be obtained prior to the first titration (week 2), prior to the intervention (week 6) and end of the study. The blood samples for the screening will be performed by the Clinical Laboratory at Boston Medical Center which will be able to provide the test result within 24-48 hours. The blood samples for the study collected after screening, will be sent to Quest Diagnostics for determining the serum 25(OH)D levels. The study design is summarized in Table 2.

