Each subject will be advised to come in for five titration visits. The purpose of these visits to establish the correct UVB dose in the SoliusONE device. At these visits, each subject will be asked questions about consumption of vitamin D, sun exposure, and whether he/she has had any adverse changes in his/her health. After the titration visit, each subject will complete a 4-week course of SoliusONE treatment. During each titration/treatment session, the study personnel will record subject's information in the application that is installed in the study personnel's smartphone. The information to be recorded include subject ID, age and sex. This allows the software to link to database and create user profiles for dosing. None of the identifiable information will be recorded in the application. Then, each subject will stand in the SoliusONE device while exposed to UVB light. Each subject will be asked to wear a swimsuit, swimming trunks (for males) or bikini (for females) while being exposed to UVB in the device. The device is large enough so that the participant is able to remove their clothing and to hang it up on a hook that is provided in the device. If they are wearing their bathing suit, they will then be exposed to the UVB light. If they have brought their bathing suit with them, they will be able to put it on in the device and then be exposed to the UVB light. They then have the option of keeping the bathing suit on and dressing or removing the bathing suit and putting on all of their undergarments and clothing before exiting the device. For those who either do not want to wear a bathing suit under their clothing or have forgot to bring their bathing suit then they will have the option of being exposed to the UVB in their underwear (males in their underwear shorts and females in their panties and bra). Each session will take approximately 2-10 minutes depending on the subject's skin type group (lighter skin type groups

require less treatment time). Before and after each treatment, the device will be cleaned using disinfectant to ensure proper hygiene.

Blood samples will be obtained from all subjects at baseline (prior to the first titration, week 2), prior to the intervention (week 6) and end of the study. Blood samples will be sent to Quest Diagnostics for determining the serum 25(OH)D levels. The study design summarized in Table 2

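### Table 2 schedules no concomitant-medication review at weeks 3–6, while the UVB dose is stepped up, and the visible plan states no action if a photosensitising drug is started

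*Combined protocol and SAP*

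**What the plan says.** Section 7.2, exclusion 4, opens "Use of medications that cause a photosensitivity reaction (including but not limited to" and lists eight named drugs as examples. Section 9 has eligibility asked about at the telephone screen, and Table 2 marks the inclusion/exclusion row at week 1 only.

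The Table 2 row "Concomitant Medications" is marked at weeks 1, 2, 7, 8, 9 and 10. The UVB row carries a separate mark for every week from 2 to 10.

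Section 6.1 states that "the risk of erythema episodes may be increased by concomitant phototoxic drugs". It adds that dosing by the individual's minimal erythema dose can reduce this risk.

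For the titration visits, Section 9 says that "each subject will be asked questions about consumption of vitamin D, sun exposure, and whether he/she has had any adverse changes in his/her health". Section 10.2 adds three software questions before each treatment: whether pinkness occurred, whether it lasted beyond three days, and whether it was painful. Section 10.4 withdraws a subject for refusal, for 25(OH)D above 100 ng/mL, or for an adverse reaction to the light.

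**The concern.** The plan treats photosensitising drugs as a reason not to expose someone to UVB and gives the reason. During dose escalation, however, the schedule has no point at which a newly started drug would be asked about, and nothing says what follows if one comes to light.

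What is at stake is a subject's skin, not the endpoint. The visible safeguards are mostly triggered by a reaction: the skin checks in Section 6.3, the software's option to lower or block the dose in Section 10.2, the end of escalation at a skin reaction in Sections 6.1 and 8, and withdrawal in Section 10.4. Each titration step is itself a wide-area exposure, because Section 9 has it that "each subject will stand in the SoliusONE device while exposed to UVB light". In the cohort study described in Section 3.1, skin typing was "followed by exposure of the underneath of one forearm to 10 successively increasing durations of exposure to UVB". Here, a change in sensitivity caused by a new drug would show as a reaction on widely exposed skin. A question asked beforehand acts earlier.

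**Working it through.** The plan gives no figure on this point to reproduce. The check sets the schedule beside the text, then uses the stated doses to see where the increases fall.

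**1. Table 2, by week**

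| Row | Marked at | Blank at weeks 3–6? |
|---|---|---|
| UVB exposure | 2–10 | No |
| Concomitant medications | 1, 2, 7–10 | Yes |
| Adverse events | 2, 7–10 | Yes |
| Sun exposure / vitamin D food checklist | 1, 2, 10 | Yes |

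Exposures without a medication mark: 4 (weeks 3, 4, 5, 6) of 9 (weeks 2–10), or 4/9 = 44%. Gap between medication marks: week 7 − week 2 = 5 weeks.

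**2. Where the dose increases fall**

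Inputs from Sections 6.1 and 8: start 10.53 to 43.07 mJ/cm², maximum 34.88 to 109.33 mJ/cm², 26–36% per step, up to five titration weeks. Assumptions: the lowest start goes with the lowest maximum, the steps are equal, and the start dose is given at week 2, which leaves four steps.

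- Lowest: 34.88/10.53 = 3.31; 3.31^(1/4) = 1.349, or 34.9% per step. Doses at weeks 2–6: 10.53, 14.21, 19.16, 25.85, 34.88.
- Highest: 109.33/43.07 = 2.54; 2.54^(1/4) = 1.262, or 26.2% per step. Doses at weeks 2–6: 43.07, 54.36, 68.62, 86.62, 109.33.

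Both step sizes lie within the stated 26–36%, so four steps fit the plan's figures. The increases then fall at weeks 3, 4, 5 and 6, the weeks with no medication mark. For a subject who reaches the maximum, the dose rises to 2.5–3.3 times the start over those visits. A subject who reacts earlier stops lower. These figures locate the escalation; they do not measure harm.

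**3. Does any text fill the blanks?**

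- Adverse events: yes. Sections 4.1.1 and 6.1 ask for reports at every visit, and Section 10.2 has an interview before each weekly exposure.
- Sun exposure and vitamin D intake: yes, in the Section 9 titration questions.
- Medications: nothing visible. Those Section 9 questions and the three Section 10.2 questions name no drugs.

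**4. Does any text state an action?**

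None of the Section 10.4 triggers is the start of a drug. Medications are recorded again at weeks 7–10, also with no stated consequence.

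**The case against.** The strongest reply is that a blank in Table 2 is weak evidence. Across the UVB visits the adverse-event row has the same pattern as the medication row, yet the text plainly requires adverse-event questions at weeks 3–6. The sun and vitamin D row is contradicted in the same way. The week 2 mark may stand for the whole titration block, or a merged cell may have been lost when the PDF was read. This stands: the blanks do not prove that nothing is asked. What separates medications from the other two rows is that no visible text supplies the question.

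Second, a reader might infer that exclusion 4 binds at entry only, since exclusion 6 reads "Plan to received significant sun exposure below the 33rd parallel during study" and exclusion 4 has no such words. The documents do not support that. Exclusion 6 concerns a plan, which is itself judged at entry. Exclusions 7 and 10 carry look-back windows and exclusion 4 carries none. Section 7.2 excludes a person from taking part, which can be read as continuing, and medications are recorded after entry. What can be said is that no continuing check or consequence is written down for the titration weeks.

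Third, the relevant material may exist unseen. Section 9 mentions subjects "answering the safety questions" on the device, and Section 11.3 refers to a visit report form. Neither is shown, nor is the consent form. Any of them could deal with new medicines.

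Fourth, escalation is already the most closely controlled part of the study: small steps that stop at a reaction, a weekly interview, a self-check for pain and redness 4–6 hours after treatment, and an instruction to call staff about side effects. The general health question might also bring up the illness behind a new prescription. All of this limits the consequence. It does not ask about a drug before the exposure is given.

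**Conclusion.** The point holds as a minor participant-safety improvement. In the visible plan, medication review is scheduled on both sides of the escalation weeks but not within them, 4 of 9 exposures carry no medication mark, and no action is given if a photosensitising drug is started, although the plan itself names the risk.

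It rests on the visible text alone. If the device questions or the visit form already ask about drugs, only a cross-reference and the action sentence remain, and the missing sentence by itself would be no more than a detail to add.

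A reader might also infer that subjects are likely to be harmed, or that the result is affected. Neither follows. The documents do not say how often subjects start such a drug, so no event rate can be given. Nothing here bears on the 25(OH)D comparison or its power, and Section 9 asks for a final blood sample before a subject is removed.

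**What to change.** In Table 2, mark Concomitant Medications at weeks 3, 4, 5 and 6, with the question asked before each exposure. In Section 7.2 or 10.4, add one sentence: a newly started drug covered by exclusion 4 is referred to the investigator before that exposure is given. If the device safety questions or the visit report form already ask this, cross-reference them in Table 2 instead of adding a question.

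The cost is one short question at four visits that already take place, plus one sentence of protocol text. The downside is that an exposure will occasionally be held while the investigator considers a new drug.

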When ultraviolet B (UVB) radiation (wavelength of 290-320 nm) from the sun is absorbed into the skin, it converts 7-DHC, which is predominantly located in the stratum spinosum and stratum basale, to previtamin D3, which is thermodynamically unstable. Over several hours it isomerizes into vitamin D3. The vitamin D3 from the skin and the vitamin D2 from food and supplements enters the circulation and are hydroxylated in the liver by a 25-hydroxylase to become 25-hydroxyvitaminD (25(OH)D), which is the major circulating form of vitamin D. 25(OH)D is hydroxylated again in the kidneys by 1alpha-hydroxylase to become 1,25-dihydroxyvitamin D (1,25(OH)2D), which is the active form of vitamin D. When calcium levels are too high, 24-hydroxylase activity increases, hydroxylating C24 and making, 24,25-Dihydroxyvitamin D (24,25(OH)2D) and 1,24,25-trihydroxyvitamin D (1,24,25-(OH)3D). This step begins the process of the degradation of both metabolites into inactive water soluble metabolites that

can be excreted in the bile. The ability to maintain 25(OH)D levels via sun exposure is influenced by the zenith angle of the sun. The zenith angle is defined as the oblique angle between the sun's rays and the earth's surface. The time of day, season, and latitude on the earth's surface all affect the zenith angle. Above 37° latitude during the months of November through February, there is a significant decrease in the amount of UVB photons hitting the earth's surface, as much as 80%-100% depending on latitude. Thus, for those living in areas at a zenith angle incompatible for producing vitamin D in the winter, they need to obtain their vitamin D via supplements and/or food containing or fortified with vitamin D.

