## 5 Study Design

This is a pilot interventional study aiming to gain experience in using of the Solius Photobiologic System that is designed to increase the serum levels of 25(OH)D in a vitamin D deficient/insufficient adult population. We will make our best effort to recruit individuals with different Fitzpatrick skin types. The study will be conducted at Boston University after it is approved by Boston University's Institutional Review Board. The use of a single location will keep uniform natural UVB exposure of the study as opposed to multiple geographic locations what would create a wide variety of natural exposures to UVB and result in a less uniform impact of this natural exposure in both study arm.

Table 1. The below guidelines will be used to make this distinction:

Table 1: Fitzpatrick Skin Types		
Skin type	Typical Features	Tanning ability
I	Pale white skin, blue/green eyes, blond/red hair	Always burns, does not tan
II	Fair skin, blue eyes	Burns easily, tans poorly
III	Darker white skin	Tans after initial burn
IV	Light brown skin	Burns minimally, tans easily
V	Brown skin	Rarely burns, tans darkly easily
VI	Dark brown or black skin	Never burns, always tans darkly

Each subject will be categorized into one of 6 Fitzpatrick skin types, type I, II III, IV and skin type V or VI. Skin types V and VI will be combined to represent the group with the darkest skin tone for subgroup analysis.

A total of 14 adult subjects with 5 skin types groups (I, II, III, IV and V/ VI) will be enrolled for vitamin D deficiency/ insufficiency screening. The screening test for 25(OH)D will be performed by the Boston

Medical Center's clinical laboratory which is able to perform the test within 24 hours. We expect at least 80% of the population in the Boston area has a level of 25(OH)D below 30 ng/ml. Thus, we expect to enroll approximately 14 subjects with different group skin types to enroll 10 vitamin D deficient or insufficient subjects in this study to receive UV exposure by the Solius Photobiologic System. The device will have a strip of colored LED installed inside the light towers. Both UV lamps and purple LED will turn on during the treatment.

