## 12 Statistical Plan

### 12.1 Statistical analysis

Data will be analyzed using the statistical software package SPSS (SPSS Institute, Chicago, USA). Serum levels of 25(OH)D will inspect for normal distribution using the Kolmogorov-Smirnov test, homogeneity of the variance (Levene-test), and outliers. The results will present as mean±standard deviation, or median.

Serum levels of 25(OH)D will be compared before and after the study using the paired Student's t-test (for normal distribution) or Wilcoxon test for repeated measures. Also, controlling for putative confounders such as skin type and sex, we will employ univariate general linear models (GLM) for the 25(OH)D levels. Significant P-value will consider <0.05.

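### The sun-exposure exclusion covers only planned in-study travel below the 33rd parallel, with no look-back for sun and no stated analysis use of the sun data collected

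*Combined protocol and SAP*

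**What the plan says.** Section 7.2, exclusion 6, excludes a subject who meets this description: "Plan to received significant sun exposure below the 33rd parallel during study". Three conditions must hold together: the exposure is planned, it falls within the study, and it lies south of 33 degrees. The text gives no basis for 33.

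Exclusion 7 in the same list reads "Used tanning or phototherapy devices within the last 30 days". It looks back in time, but only for artificial sources.

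The background (section 3.1) works with a different latitude: "Above 37° latitude during the months of November through February, there is a significant decrease in the amount of UVB photons". It puts the loss at "as much as 80%-100% depending on latitude".

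Section 5 relies on the choice of site: "The use of a single location will keep uniform natural UVB exposure of the study".

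Sun exposure is recorded. Table 2 schedules a "Sun exposure/ Vit. D food checklist" at weeks 1, 2 and 10, and section 9 says that at the titration visits "each subject will be asked questions about consumption of vitamin D, sun exposure". The analysis in section 12.1 is a paired before-after comparison, plus general linear models "controlling for putative confounders such as skin type and sex". It does not mention sun exposure or travel.

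**The concern.** Every subject receives UVB and there is no control arm, so nothing in the comparison subtracts vitamin D made from other UVB. Two routes are left open.

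- **During the study.** A subject planning heavy sun between 33 and 37 degrees is eligible. By the protocol's own account, that band is not part of the region where winter UVB is lost. Any rise between the week 2 and week 10 samples is attributed to the device.
- **Before the study.** A subject just back from a sun trip is eligible if 25(OH)D is below 30 ng/mL. If the level is still raised at week 2 and then fades, the change attributed to the device is too small.

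The two errors act in opposite directions, and with 8 to 10 subjects a single traveller can move the mean. Section 3.2 says a more extensive study is to follow, which may inherit both the estimate and the criteria.

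**Working it through.** **1. The rules side by side**

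| Source of UVB | In the period before entry | During the study |
|---|---|---|
| Tanning or phototherapy device | Excluded if within 30 days (exclusion 7) | Not addressed by exclusion 7 |
| Sun below 33 degrees | No rule | Excluded if planned and significant (exclusion 6) |
| Sun at 33 to 37 degrees | No rule | Allowed |
| Sun above 37 degrees, including the site | No rule | Allowed; UVB loss described for November to February only |

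The allowed band is 37 − 33 = 4 degrees.

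**2. The plan's own sample size (section 12.3)**

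Inputs: mean difference 6 ng/mL, SD of differences 4, two-sided alpha 0.05, power 90%, stated n = 8.

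- Normal approximation: [4 × (1.960 + 1.282) / 6]² = 4.67, rounded up to 5. Adding 1.960²/2 = 1.92 gives 6.59, rounded up to 7.
- Exact paired t: n = 7 gives 90.8% power and n = 8 gives 95.1%.

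The stated 8 is sufficient, and nothing in this point changes it.

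**3. Effect of one traveller on the mean change**

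The documents give no travel effect. Assume one of 8 completers gains an extra x ng/mL, with x = 8 and a range of 4 to 12. The shift in the mean is x/8.

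| x (assumed) | Shift | Share of the planned 6 | Share of the 4.4 in the earlier cohort |
|---|---|---|---|
| 4 | 0.5 | 8% | 11% |
| 8 | 1.0 | 17% | 23% |
| 12 | 1.5 | 25% | 34% |

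The 4.4 is 27.2 − 22.8, from the six-adult cohort in section 3.1. For scale, the standard error of the mean change under the plan's inputs is 4/√8 = 1.41 ng/mL.

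**4. Effect on the test**

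Suppose the device has no effect and outside sun shifts the group mean by 1 ng/mL, with the SD still 4. The chance of a significant increase is then 8.9% at n = 8 and 10.6% at n = 10, against a nominal 2.5% in that direction.

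That applies when the shift is spread over the group. A single traveller also widens the spread: the expected variance becomes 16 + x²/8, so for x = 8 the SD is √24 = 4.90. Simulating 8 changes with mean 0 and SD 4, one of them raised by 4, 8 or 12 (1,000,000 repeats each), gives about 4.1%, 4.3% and 3.4%. One traveller therefore harms the estimate more than the false-positive rate.

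**5. The baseline route**

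In the sponsor's earlier study of military personnel (section 3.1), the phototherapy median was 30.0 ng/mL at month 3 and 27.0 at month 4. A level raised by UVB can therefore fall by about 3 ng/mL between those visits. One of 8 subjects falling by 3 lowers the mean change by 3/8 = 0.38 ng/mL. If the group mean change were 5 instead of 6, power at n = 8 would drop from 95.1% to 85.6%.

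**6. Whether covariate adjustment could deal with it**

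With skin type in the five groups of section 5 (4 parameters), sex (1) and an intercept (1), a model for change at n = 8 leaves 8 − 6 = 2 residual degrees of freedom. There is no useful room for a sun-exposure term. That leaves eligibility and a with-and-without display as the practical tools.

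**The case against.** The strongest reply is that 33 and 37 degrees serve different purposes. A reader might infer that exclusion 6 contradicts the protocol's own threshold. The documents do not support that. The 37-degree figure is background, tied to November through February, and describes where winter UVB falls. It is never set as an eligibility standard. What stands is narrower: 33 is unexplained, and 37 is the only latitude for which the protocol offers any reasoning.

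It also follows that the latitude change is incomplete. The study runs over 6 months with no fixed season. Outside those four months the protocol describes no comparable UVB loss at the site, so ordinary local sun may matter as much as travel. This is correct and limits what the fix can claim.

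Third, the plan is not unguarded. Exclusion 6 removes the most southerly planned travel, the limit of 30 ng/mL screens out some recently sun-exposed people, sun exposure is asked about, and the covariate list in section 12.1 is open-ended. These are partial protections. No stated rule or analysis uses the sun-exposure answers.

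Fourth, the size is assumed. The central value of 8 ng/mL is nearly twice the mean rise of 4.4 after four weekly exposures in the earlier cohort, and nothing indicates how likely travel is. A shift of 1.0 is below the standard error of 1.41 and would not overturn a true effect of 6. That is fair, and it keeps this a modest point. The baseline route is also conservative for a claim of benefit, but it still distorts the estimate carried forward.

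**Conclusion.** The point holds as a modest, cheaply corrected gap in eligibility and analysis. Natural sun is restricted only when planned, during the study and south of an unexplained latitude. There is no look-back for sun although there is one for devices, and the sun-exposure data have no stated use. In this single-arm design the result can be biased upward by in-study travel or downward by travel just before week 2.

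On the assumption that one of 8 completers gains an extra 4 to 12 ng/mL, the mean change moves by 0.5 to 1.5 ng/mL, or 8% to 25% of the planned 6. The travel effect and the number of travellers are assumptions; the number of completers and the planned difference are from section 12.3.

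Two stronger readings should be avoided. Travel does not itself lower 25(OH)D; a fall arises only as an earlier rise fades. Nor do the documents show that travel would reverse the study's conclusion or that section 5's reliance on one site fails altogether. That passage contrasts one site with several, and travel only weakens it.

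**What to change.** **Eligibility.** Reword exclusion 6 to cover significant sun-travel exposure below the 37th parallel, either in the 30 days before screening or planned during the study. Both figures are already in the protocol. The documents do not show that 30 days is a full washout for 25(OH)D, so the window should be described as consistent with exclusion 7, not as proven. If the sponsor prefers to keep 33 degrees, state the reason and still add the look-back.

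**Analysis.** In section 12.1, use the sun-exposure answers already collected to present the paired result with and without any subject who reports such exposure, and keep that subject in the safety data. The form needs to capture place and dates for this to work.

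**Limitation.** State that local sun, particularly outside November to February, is not controlled by this criterion.

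**Cost.** One line in the criteria and in the telephone screen, one extra line in the results, and a few otherwise eligible travellers turned away. The sample size does not change.
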